The two currently licensed vaccines designed to prevent HPV infection, have been tested in large clinical trials. There is a bivalent vaccine against HPV 16 and 18 (GlaxoSmithKline, GSK) and a quadrivalent vaccine against HPV 6, 11, 16 and 18 (Merck). In addition, a 9-valent vaccine is currently being investigated in large scale clinical trials, with positive safety, immunogenicity and efficacy data under review by the FDA. These vaccines are produced as virus-like particles (VLP's) based on the L1 capsid protein gene of the virus inserted in insect or yeast vectors. These proteins self-assemble into protein shells with identical configuration to the native virus, but without DNA, and so are deemed subunit, protein vaccines. Safety, efficacy, and immunogenicity data on these vaccines in HIV-negative populations of young women are based on clinical trials conducted by GSK and Merck, respectively, with some follow up post-licensure trials now in progress. Both have shown remarkable safety profiles in otherwise healthy young HIV-negative women, with limited local injection site reactions as the primary side-effect and no evidence for differences in serious adverse events between vaccine and placebo arms.⁶⁵

Immunogenicity to the quadrivalent vaccine has been well studied in HIV-negative populations, showing that anti-HPV 6, 11, 16 and 18 geometric mean titers (GMT) were highest at month 7 (1 month following the final dose 3). Anti-HPV GMT's declined thereafter but reached a plateau at month 24 and remained stable through 5 years.^{66,67,68} In the original immunogenicity study by Villa et al.,⁶⁷ 100% of the subjects who were antibody negative to the relevant HPV type at baseline had a detectable antibody response at month 7 to HPV 6, 11, 16 and 18 respectively. These levels were 10-to 10⁴-fold higher than natural antibody levels in placebo recipients who were vaccine type positive at baseline.

8. **HPV vaccine implementation**

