Antibody response to HPV types 6, 11, 16 and 18 has been collected and analyzed on over 1500 serology samples for months 0, 7, 12, 18 and 24. Seroconversion rates at month 7 were approximately 93-98% in this HIV-positive population, much higher than anticipated. However, peak Geometric Mean Titres (GMT) were lower than in HIV negative populations. In addition this was associated with a significant decline in antibody levels by month 24, particularly to HPV18. Similar to our findings, Kahn et al., also showed that level of antibody was lower in individuals not on cART in their open label 16-23 year old study of 99 women given the q HPV vaccine.⁸⁰ Of note, we also observed statistically significantly higher levels of incident and persistent infections of vaccine containing types in a short term follow up period. This preliminary data outlines the importance of following this established cohort for long-term immunogenicity. When directly comparing the school based vaccine target age of 9-13 years, the HIV positive girls had a statistically significantly lower peak GMT than age matched HIV comparators.^{81,82} Similar studies conducted by other investigator groups have preliminary data available as well. Weinberg et al, showed that in HIV infected 7-12 year old children, there was a good seroconversion rate at > 94% but noted that the level of antibody to HPV18 was less than for the other genotypes. They also added a fourth dose of the vaccine which demonstrated an appropriate anamnestic response suggesting that should a booster be deemed necessary it should function to appropriately enhance the antibody response.⁸³ A South African based study of the bivalent vaccine demonstrated safety and 100% seroconversion to the vaccine containing serotypes regardless of CD4, HIV viral load and HIV clinical stage of disease.⁸⁴

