16.0 STATISTICAL ANALYSIS

1. Statistical Analysis Plan

Demographics: Characteristics of the study population will be described with frequencies and proportions for categorical variables, means and standard deviations for normally distributed continuous variables and medians and interquartile ranges for skewed continuous variables.

2. Primary Analysis

For each of the four vaccine containing HPV types, antibody response will be summarized using GMT's calculated for age specific groups within the HIV-positive cohort. Specific age groupings have been chosen to permit age matched HIV comparisons.

- a) Antibody response for subjects aged 9-13 and those aged 16-26 will be compared to the individual patient level data from an HIV-negative cohort 86 using Wilcoxon rank-sum tests. The age adjusted fold-difference in GMT

between HIV-positive and HIV-negative populations will be calculated using generalized linear models. For women over age 26, the type specific HPV GMT will be compared to GMTs in the published literature using a sign test.

- b) Within the HIV-positive cohort, predictors of decline from peak antibody response among HIV-positive girls and women will be determined using generalized linear models. Potential covariates to be considered in these models are age, HSV-2 status, substance use, CD4 count, HIV viral load and antiretroviral status at the time of first vaccination, and CD4 nadir.
- c) Longitudinal analyses will be conducted to describe the effect of HIV on antibody response at the visits at 36, 48, 60, 72, 84, and 96 months post first vaccine dose. Generalized estimating equation (GEE) models with a unity link will be used to adjust for correlation among repeat observations within study participants. Individual level data on HIV-negative girls and young women will be available at 36, 48, 60, 72, 84 and 96 months post first vaccine dose. After adjusting for age, an interaction between HIV and time since first dose will be included in the model to test for a difference in the degree of waning of response in addition to the strength of the initial response. GEE models will also be fit for the HIV-positive girls and women alone to examine the associations.

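### Section 16.2(c) claims to address initial response as well as waning, but the data it names start at month 36, so it identifies only the HIV gap from month 36 and the slope difference after it

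*Combined protocol and SAP*

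**What the plan says.** Section 16.2(c) sets out a longitudinal GEE analysis "to describe the effect of HIV on antibody response at the visits at 36, 48, 60, 72, 84, and 96 months" after the first dose. For the comparator it states: "Individual level data on HIV-negative girls and young women will be available at 36, 48, 60, 72, 84 and 96 months" after the first dose. After age adjustment, an HIV by time-since-first-dose interaction is added "to test for a difference in the degree of waning of response in addition to the strength of the initial response".

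The neighbouring items do different work:

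- Item (a): "Antibody response for subjects aged 9-13 and those aged 16-26 will be compared to the individual patient level data from an HIV-negative cohort". It names no time point and analyses no change over time. For women over 26 it offers only published GMTs.
- Item (b): "predictors of decline from peak antibody response among HIV-positive girls and women will be determined using generalized linear models". This is within the HIV-positive cohort only.

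Section 1.0 gives the time course. In HIV-negative vaccinees, "geometric mean titers (GMT) were highest at month 7"; titres then fell, levelled off from month 24 and held to five years. In this cohort, serology was "collected and analyzed on over 1500 serology samples for months 0, 7, 12, 18 and 24", and lower peak titres were "associated with a significant decline in antibody levels by month 24, particularly to HPV18".

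The hypothesis in Section 2.0 is a faster and larger decline in HIV-positive participants. It states no time window.

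**The concern.** Item (c) is the only analysis that compares change in titre between HIV groups. Its first named data point is 29 months after the peak (36 − 7) and 12 months after the plateau that the protocol describes in HIV-negative vaccinees (36 − 24). By the protocol's own account, the main HIV-negative decline is over before the model sees any data.

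Two misreadings follow if the item is carried out as written:

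- A null interaction could be taken as similar waning by HIV status, although any extra loss between months 7 and 36 never enters it.
- The HIV level term could be reported as a weaker initial response when it is the gap at month 36, or an extrapolation to month 0.

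Poor priming and faster loss are different scientific findings, and the hypothesis concerns the second.

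**Working it through.** The plan gives no sample size, power, alpha or titre variance for this analysis, so there is no figure to reproduce. The question is which quantities the named data identify.

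**Inputs from the documents.** Item (c) months for both groups: 36, 48, 60, 72, 84, 96. Peak: month 7. HIV-positive titres held from CTN 236: months 0, 7, 12, 18, 24. HIV-negative titres before month 36: none named in (c).

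**Notation.** Let g(t) be the HIV-positive minus HIV-negative mean log10 titre at month t. The log scale is my assumption; the plan states none for (c).

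- P = g(7), the difference at peak
- E = g(36) − g(7), the extra HIV-related loss from month 7 to 36
- d = the slope difference per year after month 36

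For t ≥ 36, g(t) = P + E + d(t − 36)/12.

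**Step 1: what the interaction contains.** From month 36 on, P and E appear only as the sum P+E. With months 36–96 only, the design in (intercept, late slope, P, E, d) has rank 4 of 5, because the P and E columns are identical. The interaction is d and does not contain E.

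**Step 2: estimability with a free mean per group and month.** A contrast is estimable if adding it as a row leaves the rank of the design unchanged.

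| Data used | Gap at month 7 | Change in gap, 7 to 36 | Late slope difference |
|---|---|---|---|
| As named in (c) | no | no | yes |
| Plus HIV-positive months 7–24 | no | no | yes |
| Plus HIV-negative month 7 as well | yes | yes | yes |

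The gap at month 36 is estimable in every row.

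**Step 3: linear time from dose 1.** If time is coded this way (the plan does not say), the HIV term is the gap extrapolated to month 0: P + E − 3d. Two assumed cases:

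- P = −0.3, E = −0.2, d = −0.05: −0.5 + 0.15 = −0.35
- P = −0.1, E = −0.4, d = −0.05: −0.5 + 0.15 = −0.35

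The first is a 2.0-fold lower peak with 1.6-fold extra early loss; the second is a 1.3-fold lower peak with 2.5-fold extra early loss. The model returns the same answer for both.

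**Step 4: how far the extrapolation reaches.** Assume a gap of −0.30 log10 at month 36 (2-fold), widening by 0.02 log10 per year.

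- Month 0: −0.30 + 3 × 0.02 = −0.24, or 1.74-fold
- Month 7: −0.30 + (29/12) × 0.02 = −0.252, or 1.79-fold

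These figures are the same whether the true month-7 gap is 1-, 1.5-, 2-, 3- or 5-fold. Now assume three consecutive annual visits per person, equal groups, entry spread over months 36 to 72, and within-person correlation from 0.9 down to 0. The standard error of the gap is then 1.6 to 4.1 times its month-66 value at month 0, and 1.5 to 3.7 times at month 7. The plateau described in Section 1.0 also makes a straight line back to dose 1 unsupported.

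**Step 5: illustration of the interaction test.** All inputs are assumed: 150 HIV-positive and 600 HIV-negative, SD 0.45 log10, correlation 0.8, three annual visits, d = 0, 5% level, 4,000 runs per case. Rejection was 5.7%, 5.6%, 5.3% and 5.1% for (P, E) = (−0.3, 0), (−0.3, −0.2), (−0.3, −0.5) and (0, −0.8). The last case is a 6.3-fold extra early loss (10^0.8). This follows from Step 1 by construction and is no claim about power.

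**The case against.** The strongest reply is that the phrase on initial response is loose wording for an ordinary model with an HIV main effect plus HIV by time. On that reading the interaction tests waning over and above a difference in level, and nothing is broken. The list of comparator months need not be exclusive either: it says which follow-up data are expected, not that earlier titres are lacking. Section 1.0 already reports a lower peak GMT in HIV-positive girls aged 9–13 than in age-matched comparators, so some early comparator data evidently exist.

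Part of this stands. The gap lies in how (c) is specified and does not show that early data are missing. The comparison at ages 9–13 makes the remedy more feasible, though the documents do not show that those titres are individual-level or extend to ages 16–26. The simulation adds nothing to the algebra, and its most extreme case assumes no peak difference, contrary to the lower peaks reported in Section 1.0.

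The core is not answered. Even on the loose reading, the level term is a month-36 gap or an extrapolated month-0 value, and neither is the initial response. Merging only the CTN 236 titres does not help, and items (a) and (b) contain no between-group analysis of change.

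It can also be said that dose matching and a paired-titre subset are separate issues. They do affect months 36–96 too, but they matter particularly once early contrasts are added.

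**Conclusion.** The concern holds and should be fixed. As specified, item (c) identifies the HIV gap from month 36 and the slope difference after it. It does not identify the difference in initial response or the difference in loss between months 7 and 36: of the three contrasts that matter for the hypothesis, one is estimable. This result needs no assumed titre values. It rests on (c) using the data it names and on the protocol's own placement of the peak at month 7. The fold figures, standard-error ratios and rejection rates above are illustrations on assumed inputs. Item (c) remains sound for waning after month 36.

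**What to change.** Amend Section 16.2(c) as follows.

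1. Add the CTN 236 titres already held at months 7, 12, 18 and 24, together with individual HIV-negative titres before month 36 from the cohorts in item (a) and Section 4.0 (Rationale), where available. State that the HIV-positive titres alone are not sufficient.
2. Model log titre with visit as a factor. Use a knot near month 24 only if HIV-negative titres exist near that month. For each HPV type report the HIV difference at month 7, the difference in change from month 7 to 36, and the difference in slope over months 36–96.
3. For the first two contrasts, compare participants with the same number of doses and schedule, or adjust for doses received. The comparator is a two-dose/three-dose study, and entry here requires only one dose.
4. Repeat these contrasts in participants with both an early and a late titre. Late titres come only from those who consent again, and some are already past the month 36 and 48 windows.
5. If early HIV-negative titres cannot be obtained, delete the reference to initial response, centre time at month 36, label the HIV term as the difference at month 36, and limit the between-group waning conclusion to the period after month 36.

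The cost is SAP wording, a merge with serology already held, and a data request whose outcome is not known in advance. No new samples or visits are needed. There will be more contrasts to report per HPV type, and the early ones may cover only some age groups and schedules, with fewer participants after matching on doses. The fallback in point 5 costs only wording and a change of time origin.

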Our study group was one of the first groups globally to study one of these vaccines in HIV-positive, immune compromised populations. As the qHPV vaccine GARDASIL™ (Merck), which contains subtypes 6 and 11 (responsible for 90% of genital warts) and subtypes 16 and 18 (responsible for 70% of cervical cancer) was the first to be licensed and available in Canada for post-licensure studies, we engaged with Merck to permit an initial study of the safety and immunogenicity of this vaccine in a cohort of HIV-positive girls and women. Data from this cohort has

provided valuable information about the health of Canadian women and girls living with HIV. At the initial screening visit more than 80% of subjects were negative to HPV genotypes 6, 11, 16 and 18, found in the qHPV vaccine. This was a higher seronegative rate than seen in a US based study in which only 55.6% were HPV 16 negative and 73.7% HPV 18 negative at baseline, despite being a younger cohort overall (N=99, mean age 21.4 years).⁷⁸ Preliminary data outlined that in our study, 17 % of HIV-positive women had low-grade squamous intraepithelial lesions (LSIL) or greater at screening and 29% had at least one strain of oncogenic HPV present. It was observed that greater numbers of oncogenic HPV types were present in those women with cervical dysplasia.⁷⁹

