4.0 STUDY DESIGN & METHODS

1. Design

This prospective longitudinal cohort study will evaluate the effectiveness of a quadrivalent HPV VLP vaccine in an HIV-positive cohort of girls and women in multiple centres across Canada.

2. Rationale

This study presents a unique opportunity to understand the long term impact of HPV vaccination in immune compromised women. Our prior study demonstrated that although women and girls living with HIV in Canada have complicated lives and have a high burden of socioeconomic disadvantages, they are very interested and committed to participating in research. This is clearly demonstrated by the degree of engagement of positive women in the National Consensus Statement on Women, Trans People and Girls and HIV Research in Canada. Our study sites across the country have been highly effective at engaging with this challenging population

through their long-standing, dedicated clinics. We have a cohort of over 400 girls and women who continue to live with their HIV disease and will require ongoing specialized HIV care for the rest of their lives. As they are just completing the first protocol out to 24 months and are for the most part still attending for care, with 94% remaining engaged with our study groups. We are confident that we can effectively re-engage them in our follow-up study. It is vital that this study be launched now while most participants are at 24-36 months from vaccine course, and key follow up timed sampling can ascertain the trajectory of antibody responses as well as the course of HPV disease.

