5.0 STUDY COHORT

1. Population

Four hundred and seven (407) HIV-positive girls and women (greater than, or equal to, age 11) attending the HIV treatment clinics in each of the 13 sites across Canada and who have enrolled in the original study “A Study of an HPV VLP Vaccine in a Cohort of HIV Positive Girls and Women (CTN 236)” will be offered participation in the study.

Inclusion Criteria

- Enrolled in CTN 236 study
- Able to give fully informed consent or assent

Exclusion Criteria

- Did not receive at least one vaccination via CTN 236, phase 1
- Cannot provide fully informed consent or assent

2. Delays and contraindications to subsequent study procedures

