11.0 SUBJECT COMPLETION AND WITHDRAWAL

Investigators or their delegates will attempt to contact those study subjects who do not return for study visits. Study personnel will make at least three attempts to contact the subject using various communication means. Each attempt should be documented in the subject source documents.

A subject completing three annual visits up to and including Month 96/Visit 13 will be considered to have completed the study.

Withdrawals will not be replaced. All withdrawals will be documented including the date of the withdrawal and the reason.

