- d) Predictors of HPV antibody seroresponse in our study population will be identified using logistic regression. This analysis is considered to be of vital importance as other vaccines have been shown to not be effective in subgroups of HIV positive individuals and could permit targeting of the proper population allowing for cost-effective use of this vaccine. The primary predictor of interest is CD4 count and justification for this is based on hepatitis B vaccination data described above. The secondary predictors of interest will include the variables: age, presence and number of strains of HPV, HIV viral load, use of HAART, use of injection drugs, and ethnicity. These predictors were chosen as ones that make the most clinical sense for potent impact on vaccine antibody response.

3. **Exploratory Analyses**

HSV analyses will employ linear or logistic regression models as appropriate, with HSV-2 serostatus as a time- updated primary predictor variable. To address these issues, we will quantify the impact of both incident (acquired within the past year) and prevalent (present at the time of diagnosis) HSV-2 co-infection on each of the primary HPV-related outcomes as described in preceding section (GMT, breakthrough HPV infections, genital tract dysplasia, and external genital warts).

Vaginal Microbiota Analysis. The output of the bioinformatics pipeline, including inventory of unique operational taxonomic unit (OTU) sequences, their taxonomic lineage and abundance, will be used to visualize and characterize the vaginal microbiota. Using various community-level analyses available as packages in R: 133

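### The seroresponse logistic regression has no defined outcome; read as month-7 seroconversion, it has at most about 8 to 28 non-responders per type for 7 to 8 predictor terms

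*Combined protocol and SAP*

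**What the plan says.** Section 16.2, item (d): "Predictors of HPV antibody seroresponse in our study population will be identified using logistic regression". The item gives this analysis special weight because it could show which HIV-positive subgroups the vaccine fails. CD4 count is the primary predictor. For the rest: "The secondary predictors of interest will include the variables: age, presence and number of strains of HPV, HIV viral load, use of HAART", followed by injection drug use and ethnicity.

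Item (d) names no visit, HPV type, cut-off or analysis set. It gives no expected number of non-responders, power, coding of predictors, model-building rule or provision for sparse events. Section 12.1.2 sets type-specific seropositivity cut-offs for the assay, but item (d) does not refer to them.

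The only response rate in the documents is in the Background, item 10: "Seroconversion rates at month 7 were approximately 93-98% in this HIV-positive population, much higher than anticipated". The same paragraph reports that antibody levels had fallen significantly by month 24, most of all for HPV 18, but gives no seropositivity rate after month 7.

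**The concern.** In a logistic regression the rarer outcome carries the information. If 93-98% respond, that is the 2-7% who do not. With few non-responders and many predictors, maximum-likelihood estimates tend to be biased away from zero and intervals become unreliable. When some predictor pattern contains no non-responder at all, the fit separates and returns no finite estimate.

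The stated purpose is to find out who responds poorly, so that vaccination can be targeted. A non-significant result from a model this sparse could be misread as evidence that no subgroup responds poorly. A large odds ratio could be an artefact of a handful of participants.

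**Working it through.** The plan states no sample size or power for item (d), so there is no figure to reproduce. The check below builds the event count from the plan's own inputs, assuming that seroresponse means month-7 seroconversion to a single type.

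**Inputs**
- Largest possible N: "Four hundred and seven (407) HIV-positive girls and women" (section 5.0, Population).
- Non-response: 100% − 98% = 2% to 100% − 93% = 7% (Background, item 10).
- Terms: CD4, age, HPV presence and number of strains (1 or 2 terms), viral load, HAART, injection drugs and ethnicity. That is 7, or 8 if presence and number are split, with ethnicity as a single term.
- Smaller denominators: "with 94% remaining engaged with our study groups" (section 4.0), so 0.94 × 407 = 383, and "Withdrawals will not be replaced" (section 11.0); "more than 80% of subjects were negative to HPV genotypes 6, 11, 16 and 18" (Background, item 10), so at least 0.80 × 407 = 326 if the analysis is limited to those negative at screening; "analyzed on over 1500 serology samples for months 0, 7, 12, 18 and 24", so about 1500 / 5 = 300 per time point if spread evenly (assumption).

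**Step 1. Non-responders = N × non-response rate**

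| N | at 2% | at 7% |
|---|---|---|
| 407 | 8.1 | 28.5 |
| 383 | 7.7 | 26.8 |
| 326 | 6.5 | 22.8 |
| 300 | 6.0 | 21.0 |

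**Step 2. Non-responders per term, N = 407**
- 8 terms: 8.1 / 8 = 1.0 to 28.5 / 8 = 3.6.
- 7 terms: 8.1 / 7 = 1.2 to 28.5 / 7 = 4.1.
- For comparison, five per term with 8 terms needs 40 / 407 = 9.8% non-response, and ten per term needs 80 / 407 = 19.7%.

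**Step 3. Detectable odds ratio (OR) for CD4**

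Hsieh approximation, two-sided 0.05 and 80% power (both assumed): OR per SD = exp[(1.96 + 0.84) / √(N p (1 − p)(1 − R²))], where p is the non-response rate and R² measures how far the other predictors explain CD4.
- p = 2%, R² = 0: exp(2.80 / √7.98) = 2.70. With R² = 0.2: 3.03.
- p = 7%, R² = 0: exp(2.80 / √26.5) = 1.72. With R² = 0.2: 1.84.

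**Step 4. Binary predictors**

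Power of a two-proportion comparison for a predictor held by 10-20% of participants (assumed), with overall non-response fixed:

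| | 2% non-response | 7% non-response |
|---|---|---|
| OR 2 | 18-20% | 31-40% |
| OR 3 | 35-39% | 62-75% |

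These come from a normal approximation with the pooled variance under the null, which is generous when the exposed group holds so few events.

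**Step 5. Simulation of the joint model**

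N = 407, 9 terms (one more than listed, to allow ethnicity two indicators), 500 runs per setting, covariate distributions assumed:

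| Non-response | Power for CD4, OR 1.5 per SD | Power for CD4, OR 2 per SD | Separated or did not converge |
|---|---|---|---|
| 2% | 16% | 32% | about two thirds |
| 7% | 46% | 88% | 5-7% |

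**Step 6. If a later visit is meant**

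The Summary allows each participant up to 3 of 6 visit times, so a visit averages at most 407 × 3 / 6 ≈ 204 people. With 8 terms, five non-responders per term would need 40 / 203.5 ≈ 20% seronegative, and ten would need 80 / 203.5 ≈ 39%. The documents give no later rate to compare with these.

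**The case against.** Item (d) does not say month 7. Month-7 sera were already analysed in the parent study, while this protocol collects samples at months 36 to 96, after a reported decline. At an assumed 30% non-response in all 407 there would be 0.30 × 407 ≈ 122 events, and the same simulation gives 90% power for an OR of 1.5 per SD and about 100% for an OR of 2. If 93-98% is the spread across types (an assumption), an outcome of failing at least one type would have at least about 28 events. These points stand, and they make the event count conditional. They do not remove the gap: no later rate is given, Step 6 shows that each visit has about half the cohort at best, and the plan does not say which outcome it intends. Month 7 remains the most natural reading, because items (b) and (c) already cover decline from peak and months 36 to 96, while (d) is about who responds to the vaccine.

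Item (d) also separates a primary from secondary predictors. It does not say that all enter one model, and it does not rule out penalised fitting or variable selection. That stands too: the instability applies to a standard joint fit, which the plan neither commits to nor guards against.

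Items (b) and (c) model antibody levels as continuous outcomes, so a CD4 effect would not be sought in (d) alone. This is partly right, but (b) concerns decline and (c) later visits; neither models predictors of the initial titre.

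A reader might infer that the analysis can hardly identify anyone who responds poorly, that the model has 9 to 10 terms, or that linear regression on titre is bound to be far more powerful. The documents do not support these. CD4 is detectable near 28 events; more than 8 terms requires an assumed coding of ethnicity; and any large power advantage for the titre model depends on an assumed correlation with CD4 and on an uncensored titre that itself generates the responder status. Responder status is also a defensible target when the question is in whom the vaccine fails.

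**Conclusion.** The concern holds in conditional form. If seroresponse means month-7 seroconversion to a single type, there are at most about 8 to 28 non-responders among 407 for 7 to 8 listed terms, about 1 to 4 per term, and fewer with realistic denominators. A standard model with all predictors would then be unreliable near 2% non-response. For binary predictors at an OR of 2, power stays at or below about 40% across the whole range. For CD4 the picture is mixed: poor near 2%, but adequate near 7% for an OR of about 1.7-1.8 per SD or more.

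The counts follow from the documents once the month-7 reading is adopted. The power and separation figures rest on assumed prevalences, covariate distributions, significance level and target power, and are illustrative. The lack of an outcome definition, an expected event count and a sparse-data rule holds on any reading. The plan should be changed here, given the importance it attaches to this analysis.

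**What to change.** In section 16.2, item (d):

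1. State the visit, the HPV type or types and the cut-off that define seroresponse, the analysis set, and the expected number of non-responders.
2. Fit the responder model with Firth penalisation. Pre-specify CD4 and its coding, and limit the adjusters to what the number of non-responders supports.
3. Add alongside it a regression of log10 titre, treated as censored at the assay's lower limit of detection (section 12.1.2), on the same predictors at the same visit.

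The titre model answers a related but different question, what shifts the level of response, so it should complement the responder analysis and need not replace it. The cost is SAP wording and a little more analysis of data already collected.
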